## 11.2 Study Procedures

Screening physical exam, urinalysis, serum chemistry, coagulation, and hematology that occurred *within 3 days* prior to C1D1 do not need to be repeated unless a clinically significant change in the interim is suspected.

Patients in Part 1A should be instructed to fast overnight (> 8 hours prior to their clinic visit) on Cycle 1: D1, D8, D15, and D22, C2D1, C2D8, and on Day 1 of all subsequent cycles. Patients in Parts 1B and 3 should be instructed to fast overnight (> 8 hours prior to their clinic visit) on Cycle 1: D1, D8 and D15, and on Day 1 of all subsequent cycles. Patients in Part 2 should be instructed to fast overnight (> 8 hours prior to their visit) on C1D1, D8, D15, and D22, and on Day 1 of all subsequent cycles. All patients on study should be instructed to void their bladders upon waking.

On these days, patients will undergo the pre-dose assessments, and receive the INCB001158 dose in the clinic. Recommendations on meals can be found in the Meal Recommendations section of the Study Reference Manual. The evening dose will be self-administered by the patient after all post-dose activities have been completed.

A detailed breakdown of the visit schedule and sample collection time points can be found in [Attachments 1A](#) and [1B](#).

### 11.2.1 Cycle 1

During Cycle 1, patients will undergo the following procedures:

- AE Monitoring
- Recording of concomitant medications
- Vital signs and weight
- Symptom-directed physical exam
- ECOG Performance status evaluation
- Clinical laboratory evaluation (hematology, coagulation, serum chemistry, ammonia, and urinalysis)
- Plasma sample collection for PK [REDACTED] analysis ([Attachment 2](#))  
[REDACTED]
- Urine sample for measurement of urine orotic acid levels
- Duplicate ECG with QTcF between 2-4 hr post-dose
- Administration of INCB001158.
- Part 1b and Part 3 patients will also receive pembrolizumab administration in the clinic on Day 1 of each 21-day cycle.

#### 11.2.1.1 Part 1a and 1c Only: Cycle 1 Day 1 and Day 15

Patients in Parts 1a and 1c will have a full pharmacokinetic (PK) and pharmacodynamic evaluation on Cycle 1 Day 1 following a single dose of INCB001158. Dosing on the BID schedule will commence on Cycle 1 Day 2.

On Cycle 1 Day 1 and Day 15, patients will arrive at the clinic in a fasted state and will take their assigned dose of INCB001158 after predose assessments have been collected. Blood for PK and pharmacodynamic evaluation will be taken according to the schedule in [Attachment 2](#). Once predose assessments have been completed, patients will take INCB001158 with a full glass of

water. Patients can eat breakfast 2 hours after taking INCB001158. **In Part 1a and 1c only, no second dose of drug will be provided on Cycle 1 Day 1.**

### 11.2.2 Cycle 2 and All Subsequent Cycles

A detailed breakdown of the visit schedule and sample collection time points for Cycle 2 and subsequent cycles can be found in [Attachments 1](#) and [2](#). Patients will return to the clinic and undergo the following procedures:

- AE monitoring
- Recording of concomitant medications
- Vital signs and weight
- Symptom-directed physical exam
- Clinical laboratory values (hematology, coagulation, serum chemistry, ammonia, and urinalysis)
- Urine sample for measurement of urine orotic acid levels
- ECOG performance status evaluation

█

█

- Administration of INCB001158.
- Part 1b and Part 3 patients will also receive pembrolizumab administration in the clinic on Days 1 of each 21-day cycle.
- A postdose tumor biopsy will be obtained from all patients who have consented to the tumor biopsy and for patients enrolled in the backfill cohorts. Coagulation tests must be performed and evaluated within 24 hr prior to all biopsy procedures.
- Radiographic evaluation (e.g., diagnostic CT or MRI) of tumor burden will occur approximately every 8 weeks (Parts 1a and 2) or every 9 weeks (Parts 1b and 3). The same method of evaluation should be used throughout the course of the study. The scans and redacted reports will be collected and sent to a central reader for exploratory evaluation.

#### 11.2.2.1 Part 1a Only: Cycle 2 Days 1-8

Patients in Part 1a will participate in a food effect assessment. During Cycle 2 Day 1 through Day 7, patients will be taking their INCB001158 dose with food. Recommendations on meals

can be found in the Meal Recommendations section of the Study Reference Manual. On Cycle 2 Day 8, patients will arrive at the clinic in a fasted state and will be provided breakfast in the clinic. Patients will take their assigned dose of INCB001158 immediately after eating breakfast. Blood for PK and pharmacodynamic evaluation will be taken over 8 hours, according to the schedule in [Attachment 2](#).

**11.2.2.2 Part 2d Only**

[REDACTED]

**11.3 Other Schedules and Procedures**

For Study Parts 1a and 2, radiographic evaluation of tumor burden (e.g., diagnostic CT/MRI) will occur at Screening and approximately every 8 weeks after study initiation, or more frequently as clinically indicated.

For Study Parts 1b and 3, radiographic evaluation of tumor burden (e.g., diagnostic CT/MRI) will occur at Screening and approximately every 9 weeks after study initiation, or more frequently as clinically indicated.

Optional tumor biopsies may be obtained at variable time points as advised by the Investigator and Medical Monitor and agreed by the patient.

During study treatment, urine pregnancy tests will be performed locally as medically indicated, or per country-specific requirement. If a urine pregnancy test is positive, then the results should be confirmed with a serum pregnancy test.

If the serum pregnancy test is negative after a urine test was positive, then the investigator will assess the potential benefit/risk to the subject and determine whether it is in the subject's best interest to resume study treatment and continue participation in the study.

#### **11.4 End of Treatment (EOT)**

The End of Treatment (EOT) visit must occur within 28 days of treatment discontinuation and prior to initiation of any new anti-cancer therapy/regimen. All patients discontinuing study treatment for any reason should undergo the following EOT procedures:

- AE monitoring
- Recording of concomitant medications
- Vital signs and weight
- Complete physical examination
- ECOG performance status evaluation
- Clinical laboratory values (hematology, coagulation, serum chemistry and urinalysis)
- Urine pregnancy test for women of child-bearing potential
- Duplicate 12-lead ECG with QTcF
- Radiographic evaluation (e.g., diagnostic CT or MRI) of tumor burden. Patients who discontinue from study due to objective findings of progressive disease during an on-treatment evaluation do not need to have repeat scans. CT or MRI is required for all patients who have not had at least 1 post-baseline image.

#### **11.5 Follow-Up**

##### **11.5.1 Safety Follow-Up**

The safety follow-up period is the interval between the EOT visit and the scheduled follow-up visits, which should occur 30 to 37 days (all patients) and 90 to 97 days (Parts 1b and 3 only) after the final dose of study treatments.

Adverse events (all patients) and SAEs (Parts 1a and 2 only) must be reported up until the date of the 30-day follow-up visit, or until toxicities resolve, return to baseline, or are deemed irreversible, whichever is longer.

Serious adverse events (Parts 1b and 3 only) must be reported up until the date of the 90-day follow-up visit, or until toxicities resolve, return to baseline, or are deemed irreversible, whichever is longer.

Reasonable efforts should be made to have the patient return for the follow-up visits and report any AEs that may occur during this period. If the patient cannot return to the site for the safety follow-up visit (eg, lives far away), the patient should be contacted by telephone for assessment of AEs and SAEs. Sites should document this contact in the source.

If a patient is scheduled to begin a new anticancer therapy before the end of the 90-day safety follow-up period, the safety follow-up visit should be performed before new anticancer therapy is started. Once new anticancer therapy has been initiated, the patient will have completed the follow-up period.

### **11.5.2 Disease Status Follow-Up**

Patients who discontinue study treatment for reasons other than disease progression will continue to be assessed for their disease status during the follow-up phase and should continue to have tumor assessments every 8 weeks (monotherapy) or 9 weeks (pembrolizumab combination) until a new cancer therapy is started, disease progression, death, withdrawal of consent, or the end of the study.

### **11.6 Screen Failures**

Patients who sign an informed consent form, are not assigned to a treatment, and do not receive either INCB001158 or pembrolizumab are defined as screen failures. For all screen failures, the Investigator will enter the screening number, patient initials, and reason(s) for screen failure into the electronic data capture (EDC) system. These data will also be retained in the Investigator's study files and can be printed by the site in log format at the end of the study.

### **11.7 Safety Evaluation**

Routine safety and tolerability will be evaluated from the results of reported signs and symptoms, scheduled physical examinations, vital sign measurements, duplicate 12-lead ECGs (including QTcF intervals), and clinical laboratory test results.

More frequent safety evaluations may be performed if clinically indicated or at the discretion of the Investigator. All AEs will be recorded from the time the patient receives the first dose of study treatment up to 28 days after the last dose.

#### **11.7.1 Physical Examination**

Complete physical examinations will be performed by a licensed physician (or physician's assistant or nurse practitioner) at Screening and End of Treatment. Symptom-directed physical

exam are required as clinically indicated. Please refer to the Schedule of Study Assessments ([Attachment 1](#)).

### 11.7.2 Vital Signs

Vital signs (blood pressure, respiratory rate, pulse rate, and temperature) will be obtained in the sitting position. All patients should be sitting for 3-5 min prior to obtaining vital signs.

Orthostatic vital signs will be measured on Cycle 1 days 1 and 15 at predose and 4 hrs post dose during the dose escalation (Part 1a). Due to the absence of an effect on orthostatic vital signs, orthostatic vital signs will only be required for patients enrolled in Part 1a. If effects on blood pressure are eventually noted, additional orthostatic vital sign monitoring will be re-introduced in Parts 1b, 2 and 3.

In Parts 1b and 3, on the day of pembrolizumab infusion, vital signs will be obtained pre-infusion, 15 minutes after the start of the infusion, at the end of the infusion, and 15 minutes after completion of the infusion. Vital signs should be collected  $\pm$  5 minutes from the scheduled times noted above.

### 11.7.3 Electrocardiograms

[figure not shown]
Patients should rest in the supine position for at least 5 min before each 12-lead ECG recording is started. Duplicate ECG recordings must be performed using a standard, high-quality, high-fidelity electrocardiograph machine equipped with computer-based interval measurements. The average of values will be used for Inclusion/Exclusion and AE reporting purposes.

[figure not shown]
For safety monitoring purposes, the ECG must be reviewed, signed, and dated promptly by a qualified physician (or qualified physician's assistant or nurse practitioner) and any clinically important finding recorded on the appropriate eCRF. The Investigator is responsible for providing the interpretation of all ECGs. The results will include heart rate (HR), R-R interval (RR), PR interval, QRS interval, QT interval, and QTcF interval. The corrected QT interval will be corrected for respiratory rate according to the following formula:

[figure not shown]
$$\text{Fridericia's formula: } QTcF = QT/RR^{0.33}$$

### 11.7.4 Safety Laboratory Determinations

[figure not shown]
Laboratory evaluations will be performed as noted in the Schedule of Study Assessment ([Attachment 1A](#) and [1B](#)).

## 11.9 Pharmacokinetic Evaluation

### 11.9.1 Blood Collection

Plasma PK samples will be used to measure concentrations of INCB001158. [REDACTED]

[REDACTED] Blood samples for PK analysis should be collected at the requested time ([Attachment 2](#)). The exact actual time of collection must be noted in the source documents and eCRFs.

### 11.9.2 Intensive PK Sampling

Patients enrolled in Parts 1a and 1c will participate in the intensive PK sampling schedule. Plasma PK samples will be collected on Cycle 1, Days 1 and 15 at pre-dose and post-dose at 0.5, 1, 2, 4, 6, 8, and 12 hr.

In addition, patients assigned to the intensive PK group in Part 1a only will participate in an assessment of the effect of food on INCB001158 PK. On Cycle 2 Days 1 through 7, patients will take their INCB001158 doses immediately following a meal. On Cycle 2, Day 8, patients will arrive at the clinic fasted. The pre-dose assessments will be completed and the patient will take INCB001158 immediately after eating a modest breakfast. PK samples will be drawn at 0.5, 1, 2, 4, 6, and 8 hr after taking the morning dose. The evening dose will be taken per protocol 12 hr after the morning dose. Refer to the PK [REDACTED] Sampling Schedule ([Attachment 2](#)) for time points and blood volumes to be collected.

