Upon opening Part 1b, a minimum of 3 patients will receive pembrolizumab (200 mg IV Q3W) in combination with INCB001158. Enrollment in Part 1b is limited to patients that would be eligible for the Expansion Cohorts in Part 3. In Part 1b, the starting dose of INCB001158 will be 50 mg BID, which is 2 dose levels below the recommended monotherapy Phase 2 dose of 100 mg BID identified in Part 1a of this study. Dose escalation will proceed according to the Dose Escalation Schedule that is being employed in Part 1a (Table 5.1-1). A dose level shall not be enrolled in Part 1b until it has been demonstrated to be at or below the monotherapy MTD in Part 1a.

*Part 1c. INCB001158 in Combination with Pembrolizumab in Patients with Moderately Impaired Renal Function*

At US sites only, Cohort 1c will enroll 6 patients who have moderately impaired renal function (defined as CrCl 30-49 mL/min calculated by the Cockcroft-Gault formula) AND meet eligibility criteria for any of the combination expansion cohorts (3a through 3h). The safety of INCB001158 in combination with pembrolizumab was fully characterized with a comprehensive dose escalation in patients with CrCl  $\geq 50$  mL/min. Additionally, pembrolizumab did not have

any effect on the PK of INCB001158. Therefore, Cohort 1c will evaluate a reduced dose of INCB001158 50 mg BID (determined using population PK modeling) in combination with pembrolizumab in order to determine a pharmacodynamically active dose in patients with moderately impaired renal function.

Based on population PK modeling, a dose of INCB001158 50 mg BID in patients with CrCl 30 to 49 mL/min is predicted to achieve INCB001158 AUC/Cmin values to fall within the known safe exposure range corresponding to doses at the established RP2D of 100 mg BID (see Section 10.2). Six patients meeting eligibility criteria for Parts 3a through 3h will be enrolled at the reduced dose of 50 mg BID to obtain full PK, PD (see Attachment 2C), and safety data. All data collected during the first cycle (21 days) will be evaluated, along with the population PK modeling data, to determine the INCB001158 dose in patients with moderately impaired renal function that most closely approximates the PK parameters of the RP2D of 100 mg BID in patients with normal renal function and specifically meets the following PK and PD criteria:

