- At least half of the patients (minimum of 2 patients) achieve the target exposure leading to continuous inhibition of extracellular arginase 1 by > 90% (a trough [Cmin] plasma concentration of INCB001158 at steady state of  $\geq 1$   $\mu$ M), AND/OR
- At least half of the patients (minimum of 2 patients) achieve a 2.5-fold increase in fasting plasma arginine at Cycle 1 Day 15 predose relative to their baseline (Cycle 1 Day 1 predose) value.

Population PK modeling showed a highly predictable, linear, inverse relationship between CrCl and AUC, Cmax, and half-life for INCB001158 (see Section 10.2.2.1). Therefore, if the PK-PD criteria specified above are not met at the 50 mg BID dose, population PK modeling will be used to determine whether a lower dose (25 mg BID) or a previously evaluated intermediate dose (75 mg BID) would more closely approximate PK parameters for the established RP2D of 100 mg BID. Cohort 1c patients who do not complete all planned PK assessments or have treatment discontinuation or interruptions during the first 21 days of dosing will be replaced until 6 evaluable patients have been accrued to the cohort. Patients meeting the pre-specified PK and PD criteria will be counted towards the Simon 2-stage efficacy assessment in their respective Part 3 expansion cohorts, provided these have not fully enrolled at the time data from these patients become available.

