**ATTACHMENT 2A: PHARMACOKINETIC [REDACTED] SAMPLING SCHEDULE FOR PART 1A**

Detailed instructions on sample collection and shipment can be found in the Laboratory manual.

Study Day (C=cycle, D=Day)	INTENSIVE SAMPLING PK GROUP: Part 1a Patients Only					
	Time point 	PK [REDACTED]	Amino Acid Panel 	[REDACTED]	Urine sample for Orotic Acid 	Plasma Ammonia 
Screening						
C1, D1 & D15	Predose	3 mL	2 mL		2 mL	X
C1, D1 & D15	0.5 hr	3 mL				
C1, D1 & D15	1 hr	3 mL				
C1, D1 & D15	2 hr	3 mL				X
C1, D1 & D15	4 hr	3 mL				
C1, D1 & D15	6 hr	3 mL	2 mL		2 mL	X
C1, D1 & D15	8 hr	3 mL				
C1, D1 & D15	12 hr	3 mL				
C1, D2	Predose	3 mL	2 mL		2 mL	X
C1, D8	Predose	3 mL	2 mL		2 mL	X
C1, D22	Predose	3 mL	2 mL		2 mL	X
C2, D1	Predose	3 mL	2 mL		2 mL	X
C2, D8	Predose	3 mL	2 mL		2 mL	X
C2, D8	0.5 hr	3 mL				
C2, D8	1 hr	3 mL				
C2, D8	2 hr	3 mL				X
C2, D8	4 hr	3 mL				
C2, D8	6 hr	3 mL	2 mL		2 mL	X
C2, D8	8 hr	3 mL				
C3, D1	Predose	3 mL	2 mL		2 mL	X
C4, D1	Predose	3 mL	2 mL		2 mL	X
Total sample collected		63 mL blood	20 mL blood			

1. Where applicable, the collection window is ±15 minutes. Post dose time points for urine orotic acid collection window are ± 1 hour. The collection window for the C1D1 and C1D15 12 hr PK sample is ± 1 hr. The actual sample collection time will be entered in the EDC.

[REDACTED]

4. The sample collection time points may be modified if the data indicate that these samples are no longer necessary to ensure patient safety. Pre-dose orotic acid will be collected any time prior to patient's dosing. Where applicable, the post dose collection window is  $\pm$  1hr.
5. The sample collection time points may be modified if the data indicate that these samples are no longer necessary.
6. Plasma ammonia samples will be collected and sent to the sites local laboratory.  
[REDACTED]
9. 2 mL blood will be collected in to one sodium heparin tube and processed for amino acid.
10. In addition to Orotic acid samples collected through Cycle 4 Day 1 (C4D1), samples will also be collected on day one of every cycle (example, C5D1, C6D1, etc).

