**ATTACHMENT 2C: PHARMACOKINETIC [REDACTED] SAMPLING SCHEDULE FOR PARTS 1B, 1C, AND 3**

Detailed instructions on sample collection and shipment can be found in the Laboratory manual.

Study Day (C=cycle, D=Day)	SPARSE SAMPLING PK GROUP: All patients in Part 1b and 3 Below are assessments for patients enrolled in Part 1b and 3					
	Time point 	PK/ [REDACTED]	Amino Acid Panel 	[REDACTED]	Urine sample for Orotic Acid 	Plasma Ammonia 
Screening						
C1, D1	Predose	3 mL	2 mL		2 mL	X
C1, D1	Postdose	3 mL 	2 mL 		2 mL 	X 
C1, D8	Predose				2mL	X
C1, D15	Predose	3 mL	2 mL		2 mL	X
C1, D15	Postdose	3 mL 	2 mL 		2 mL 	X 
C2 D1	Predose	3 mL	2 mL		2 mL	X
C3, D1	Predose	3 mL	2 mL		2 mL	X
C4, D1	Predose	3 mL	2 mL		2 mL	X
Total sample collected		21 mL blood	14 mL blood			

Study Day (C=cycle, D=Day)	PK/PD ASSESSMENTS FOR PART 1C Below are assessments for patients enrolled in Part 1c					
	Time point 	PK/ [REDACTED]	Amino Acid Panel 	[REDACTED]	Urine sample for Orotic Acid 	Plasma Ammonia 
Screening						
C1, D1	Predose	3 mL	2 mL		2 mL	X
C1, D1	0.5 hr	3 mL				
C1, D1	1 hr	3 mL				
C1, D1	2 hr	3 mL				X
C1, D1	4 hr	3 mL				
C1, D1	6 hr	3 mL	2 mL		2 mL	X
C1, D1	8 hr	3 mL				
C1, D1	12 hr	3 mL				
C1, D8	Predose				2mL	X
C1, D15	Predose	3 mL	2 mL		2 mL	X
C1, D15	Postdose	3 mL 	2 mL 		2 mL 	X 
C2 D1	Predose	3 mL	2 mL		2 mL	X
C3, D1	Predose	3 mL	2 mL		2 mL	X
C4, D1	Predose	3 mL	2 mL		2 mL	X

1. Where applicable, the collection window is ±15 min. Post dose time points for urine orotic acid collection window are ± 1 hour. The actual sample collection time will be entered in the EDC.

[REDACTED]

4. The sample collection time points may be modified if the data indicate that these samples are no longer necessary to ensure patient safety. Pre-dose orotic acid will be collected any time prior to patient’s dosing. Where applicable, the post dose collection window is ± 1 hr.

5. Plasma ammonia samples will be collected and sent to the sites local laboratory.

[figure not shown]
[REDACTED]

[figure not shown]
7. The PK postdose sample will be collected 1-4 hours post dose.

8. The Orotic acid, amino acid, and ammonia samples will be collected 4-6 hours post dose.

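### Protocol Section 11.9.2 asks for eight PK samples on Day 15 in Part 1c, while the Part 1c table in Attachment 2C schedules two; the steady-state part of the renal comparison depends on which applies

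*Protocol*

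**What the plan says.** - **Section 11.9.2 (Intensive PK Sampling):** "Patients enrolled in Parts 1a and 1c will participate in the intensive PK sampling schedule". Then: "Plasma PK samples will be collected on Cycle 1, Days 1 and 15 at pre-dose and post-dose at 0.5, 1, 2, 4", continuing to 6, 8 and 12 h. Only the Cycle 2 food-effect assessment is restricted to Part 1a. The section closes by referring to Attachment 2 for time points and volumes, as Section 11.9.1 also does.
- **Attachment 2C, Part 1c table:** Day 1 of Cycle 1 has predose, 0.5, 1, 2, 4, 6, 8 and 12 h. Day 15 has predose and one post-dose PK sample; footnote 7 says "The PK postdose sample will be collected 1-4 hours post dose". These Day 15 PK rows are the same as in the sparse table for Parts 1b and 3.
- **Attachment 2A:** the only table with an eight-point Day 15 profile is headed "INTENSIVE SAMPLING PK GROUP: Part 1a Patients Only".
- **Section 11.2.1.1 (Parts 1a and 1c):** a full evaluation is promised for Day 1. For Days 1 and 15, "Blood for PK and pharmacodynamic evaluation will be taken according to the schedule in" Attachment 2. It adds: "In Part 1a and 1c only, no second dose of drug will be provided on Cycle 1 Day 1".
- **Section 5.1, Part 1c:** six patients are enrolled "to obtain full PK, PD (see Attachment 2C), and safety data". The replacement rule covers "Cohort 1c patients who do not complete all planned PK assessments".
- **Analysis:** Section 3.0 lists Cmax, Tmax, AUCt, AUC0-12 and CL/F at CrCl 30-49 mL/min as secondary endpoints. Section 15.2 and the Synopsis plan a descriptive comparison of Day 1 and of steady state (Days 8 and 15). Section 15.6 specifies noncompartmental analysis with Cmax and AUC ratios and 90% intervals, and names no study day for Part 1c. SAP Section 1 defers PK methods to a separate document.

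**The concern.** The protocol gives two different Day 15 schedules for the one cohort whose main purpose is pharmacokinetic, and states no order of precedence. The Day 15 PK entries are legible, so redaction does not explain the difference.

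Day 15 is the steady-state profile day in Cycle 1; Day 1 follows a single dose. Under Attachment 2C the single post-dose sample falls at or before the Tmax of about 4 h reported in Section 10.1.10, and nothing is drawn afterwards. At stake are the Day 15 Cmax, Tmax, AUC0-12 and CL/F, and hence the steady-state half of the comparison in Section 15.2.

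The replacement rule is affected too. A patient with both Attachment 2C samples on Day 15 is complete under that table and six samples short under Section 11.9.2. With six evaluable patients, this could change who is analysed.

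**Working it through.** **1. Sample counts (Cycle 1 PK samples per Part 1c patient, 3 mL each)**

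| | Day 1 | Day 15 | Total | Volume |
|---|---|---|---|---|
| Section 11.9.2 | 1 + 7 = 8 | 1 + 7 = 8 | 16 | 48 mL |
| Attachment 2C, Part 1c table | 8 | 1 + 1 = 2 | 10 | 30 mL |
| Difference | 0 | 6 | 6 | 18 mL |

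Check on the counting: the Part 1b/3 table has 7 PK samples, and 7 × 3 = 21 mL, which matches its printed total. Attachment 2A lists the same eight times for Days 1 and 15, which confirms the eight-point reading of Section 11.9.2.

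**2. What Attachment 2C leaves on each day**

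- Day 1: eight times through 12 h after a single dose, the same times and dosing pattern as Part 1a. Day 1 Cmax, Tmax and AUC0-12 can be compared with Part 1a.
- Day 15: predose and one sample at 1-4 h. The trough and the predose arginine ratio are available. Nothing is observed after 4 h, so no standard noncompartmental AUC0-12 exists; Tmax cannot be determined, and Cmax depends on when the one sample happens to be drawn.
- Day 8: no PK sample in Section 11.9.2, Attachment 1B or Attachment 2C for Part 1c, although Section 15.2 and the Synopsis name it. Part 1a has a Day 8 predose sample.

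**3. Could CL/F come from Day 1 instead?** After a single dose, CL/F = dose / AUC0-inf, and sampling stops at 12 h. Assumptions, since the documents do not give the needed figures: one compartment, constant volume, half-life inversely proportional to clearance and so scaling with the AUCs in Table 10.2-1; the reported half-life of about 6 h placed at CrCl 60, 80 or 100; absorption instantaneous, or with ka set so that Tmax is 2 or 4 h in the patient with a 6 h half-life.

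- Half-life at CrCl 40: 6 × 16,391/11,428 = 8.6 h; 6 × 16,391/8,946 = 11.0 h; 6 × 16,391/7,457 = 13.2 h.
- Share of AUC0-inf beyond 12 h: exp(-12ke) for instantaneous absorption; otherwise [ka·exp(-12ke) - ke·exp(-12ka)] / (ka - ke).
- Example, half-life 8.6 h: 2^(-12/8.6) = 38%. With Tmax 4 h (ka = 0.46 per h, ke = 0.081 per h): 46%.

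| CrCl (mL/min) | Share beyond 12 h |
|---|---|
| 50 | 31-54% |
| 40 | 38-60% |
| 30 | 48-67% |

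**4. How much of Day 15 AUC0-12 could two samples recover?** Same one-compartment model at steady state, dosing interval 12 h, Tmax setting 2 or 4 h. Carry the predose value to 12 h, so C(12) = C(0), with the post-dose sample at time t. The trapezoid is then t·(C0 + Ct)/2 + (12 - t)·(Ct + C0)/2 = 6·(C0 + Ct), against a true AUC0-12 of 1/ke per unit dose over volume.

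- Lowest case, CrCl 50: half-life 6 × 13,413/11,428 = 7.0 h, Tmax setting 4 h, sample at 1 h. C0 = 0.557 and C1 = 0.857, so 6 × 1.414 = 8.49 against 1/ke = 10.15, or 84%.
- Over CrCl 30-50 and sampling times of 1-4 h, the range is about 84-99%.

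This is a model-based approximation. The two samples themselves span only the first 1-4 h of the interval.

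**The case against.** The strongest reply is that Attachment 2C is the likelier operating schedule. Sections 11.9.1 and 11.9.2 both send the site to Attachment 2, and Section 5.1 cites Attachment 2C by name. That is fair, and it makes the second reading of the replacement rule less likely. But it leaves an explicit eight-point Day 15 instruction in Section 11.9.2, and if Attachment 2C does govern, the Day 15 profile is lost.

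The second reply is that little depends on it. Section 15.6 fixes no day for the Part 1c ratios, Day 1 remains like-for-like with Part 1a, the stated dose criteria in Section 5.1 are trough and arginine supported by population PK, and the comparison is descriptive in six patients. All of that stands. It limits the loss to the steady-state half.

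Third, the 31-67% figure describes Day 1 extrapolation and does not measure the Day 15 loss. Correct: it bears only on CL/F from Day 1. The closer measure for Day 15 is the 84-99% recovery, which is fairly mild for AUC but does not restore Tmax or a standard noncompartmental analysis.

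A reader might infer that Part 1c cannot deliver its PK endpoints or choose a dose, or that its Day 15 results must be set against Table 10.1-1. The documents support neither: Day 1 and the dose criteria are intact, and no text names that table as the comparator; Section 15.6 names patients with CrCl of at least 50 mL/min. The separate PK analysis document and the Laboratory manual were not available and may settle part of this.

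**Conclusion.** The contradiction is real and the protocol text does not resolve it: eight Day 15 PK samples under Section 11.9.2 against two under Attachment 2C, or 18 mL per patient. If Attachment 2C is followed, the Day 15 AUC0-12, the CL/F based on it, and a reliable Cmax and Tmax are not available by the noncompartmental method in Section 15.6, and the steady-state half of the Section 15.2 comparison fails on that method.

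The damage stops there. Day 1 Cmax, Tmax and AUC0-12, the Day 15 trough and arginine criteria, and population PK are unaffected. Of the two fallbacks, CL/F from Day 1 would extrapolate about 31-67% of AUC0-inf, and a two-sample Day 15 approximation would recover about 84-99% of AUC0-12. Both ranges rest on the one-compartment assumptions set out above; the counts rest on none. Who counts as PK-complete also depends on which schedule governs. The Day 8 reference is a smaller mismatch, and the documents do not show which side was intended.

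**What to change.** Reconcile Section 11.9.2 with the Part 1c table in Attachment 2C.

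- **If sampling is open:** give the Part 1c Day 15 PK rows of Attachment 2C the eight time points that Section 11.9.2 already requires, and define the planned PK assessments in the replacement rule by that table. Cost: six more 3 mL tubes per patient (18 mL), or 6 × 6 = 36 tubes and 108 mL for six patients, plus a text correction.
- **If sampling is complete:** state which schedule was followed, which patients counted as complete, and, where Attachment 2C was used, that the Part 1c Cmax and AUC ratios in Section 15.6 rest on Day 1, with Day 15 exposure taken from the trough or population PK. This belongs in Section 15.6 or the separate PK analysis document. Cost: text only.
- **Either way:** reconcile Day 8 in Section 15.2 and the Synopsis with the Part 1c schedules, which contain no Day 8 PK sample.
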